Study population	
Patients diagnosed with rheumatoid arthritis aged 18 years or older, with a disease duration of 16 weeks or more, no exclusions based on sex or therapy.
 
Patients will be randomized (1:1) to one of the following groups:
 
 - Control group: standard of care (including referral to allied health professionals for additional education/non-pharmacological support as needed), educational leaflet, completion of the RAID questionnaire at baseline and last study visit. No access to the Sidekick Health app, and no completion of the RAID questionnaire in between study visits. - Intervention group: standard of care (including referral to allied health professionals for additional education/non-pharmacological support as needed), educational leaflet and access to the Sidekick Health app, including completion of the RAID questionnaire via the app in between study visits. 
Participants who are randomized to the intervention group will be re-randomized in a 1:1-ratio to one of the following arms:
 
 - Intervention arm A: intervention with the Sidekick Health app as described above, and participants will be asked to complete a RAID questionnaire in-app once a week. - Intervention arm B: intervention with the Sidekick Health app as described above, and participants will be asked to complete a RAID questionnaire in-app once a month.
Trial Design	Investigator-initiated, open-label, parallel-group, multicenter randomized controlled trial (without IMP).
Endpoints	
Primary endpoint Difference in mean change of total ASES (Arthritis Self-Efficacy Scale) score from baseline to week $16 \pm 2w$ in the

intervention group when compared to the control group. The ASES is a patient-reported questionnaire consisting of 20 items to measure one's arthritis-specific self-efficacy across 2 subscales: self-efficacy for managing pain (PSE, range 5-50), and self-efficacy for controlling other symptoms (OSE, range 6-60). Both scores can be summed to derive a total ASES-score (range 11-110).

Secondary endpoints

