* User-behavior statistics: Sidekick Health will provide pseudonymized logged data from the app. This includes “passive” usage information such as the number of times participants logged into the app or the number of goals that were set, as well as data that were actively logged by participants relating to their physical activity, diet, stress (such as minutes spent completing relaxation exercises in the application), and sleep.

- Baseline predictors of the intervention’s effect on ASES, PCS, IPAQ-S and PSQI scores: candidate predictors include demographic characteristics, disease-related characteristics (autoantibody status, current and previous therapy, disease duration, ...), and measures of participant engagement (as previously defined).

- The evolution and fluctuation over time of scores on the RAID-questionnaire completed in the app, and its association with self-efficacy, physical activity, sleep quality, and disease activity assessed at the study visit. The RAID is a patient-reported questionnaire with 7 items scored on a 0-10 numeric rating scale, enquiring about the impact of RA on different aspects of physical and mental health. Disease activity will be assessed as in usual care, with composite scores such as the DAS28-CRP and SDAI (both are composed of the number of tender joints and swollen joints, patient’s global assessment of disease activity on a visual analogue scale VAS, and C-reactive protein CRP; the SDAI additionally includes the physician’s global assessment of disease activity).

- The association of data actively logged in the app (step counts, exercise activities, diet, sleep quality, stress level, and energy level) with the validated outcome measures RAID, IPAQ-S, PSQI, ASES, and DAS28-CRP.

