4.6 Trial Flowchart

Procedures / Assessment	Screening and randomization	Intervention period	
		During intervention	Visit 2 = Evaluation of primary endpoint
Visits / Contacts	Visit 1 = Baseline	During intervention	Visit 2 = Evaluation of primary endpoint
Timing (weeks)	Week 0		Week 16 ± 2w
Informed consent	X		
Inclusion / Exclusion criteria	X		
Randomization	X		
Downloading Sidekick Health app	X		
Demographics (age, sex), RF and ACPA status, radiographic erosions, disease duration, past and current DMARD-therapy, prior DMARD-therapy, BMI, smoking status, education level	X		
Medical and Surgical history, comorbidities (if available in the patient file)	X		
Physical examination (including TJC28 and SJC28)	X		X

Patient's global assessment (VAS)	X		X
Physician's global assessment (VAS)	X		X
HAQ	X		X
Weight / Height / BMI	X		X
Blood sampling (CRP) as part of usual care (in clinic or through patient's general practitioner)	X		X
ASES	X		X
PCS	X		X
IPAQ-S	X		X
PSQI	X		X
RAID (both control- and intervention group)	X		X
RAID (via Sidekick Health app, only in intervention group): - Intervention arm A: weekly - Intervention arm B: monthly		X	
Collecting in-app logged data concerning physical activity, sleep, diet, stress management			X

RF = Rheumatoid Factor, ACPA = Anti-citrullinated peptide antibodies, DMARD = disease-modifying antirheumatic drug, BMI = body mass index, TJC28 = tender joint count in 28 joints, SJC28 = swollen joint count in 28 joints, VAS = Visual Analogue Scale, HAQ = Health Assessment Questionnaire, CRP = C-reactive protein, ASES = Arthritis Self-Efficacy Scale, PCS = Pain Catastrophizing Scale, IPAQ-S = International Physical Activity Questionnaire short form, PSQI = Pittsburgh Sleep Quality Index, RAID = Rheumatoid Arthritis Impact of Disease

5. Selection and withdrawal of subjects

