As stated before, one arm of the intervention group will be asked to complete the RAID questionnaire on a weekly basis, the other one will do this on a monthly basis. During this phase of the study user behavior statistics will also be collected as described above (number of times the app was used, how often certain questions were answered, ...).

Visit 2 (week 16 ± 2)

- Participants in both the control and intervention groups will be asked to again complete the previously outlined questionnaires considering self-efficacy (ASES), patient-reported outcomes (RAID), physical disability (HAQ), pain catastrophizing (PCS), physical activity (IPAQ-S), and sleep quality (PSQI). Questionnaires will be completed in MyNexuzHealth or in pen-and-paper form at the outpatient clinic if not available. In addition, disease activity will again be assessed as part of routine care by way of the DAS28-CRP and SDAI scores.
- The study will end after this visit. The participants will be free to continue with the Sidekick-application at their leisure, or alternatively, to terminate the account. Upon termination of the account, all stored personal data will be removed from the application's data cloud (also see section on Data handling).

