6.3 Other investigations

Other than any investigations required as part of routine care, no additional investigations will be carried out for this study.

7. Assessment of efficacy

Efficacy of this app-based educational, monitoring, and lifestyle intervention will be studied by assessing changes in self-efficacy (ASES), physical activity (IPAQ-S) and sleep quality (PSQI), while the intervention's effect on pain catastrophizing will be studied in a non-inferiority setting to exclude any

(negative) effects of systematic PRO-registration on pain perceptions. As stated in the sections on Trial Objectives and Design, the primary endpoint will be the difference in mean change of total ASES-score from baseline to week 16 ± 2 w in the intervention group when compared to the control group, while the intervention's effect on pain catastrophizing was chosen as a secondary endpoint. Sample size calculations were based on obtaining 80% power for both the primary and the secondary endpoint, as outlined in section 9.

In addition to the information obtained from the questionnaires, we will also study participants' continued engagement with the app and its possible effects on intervention efficacy as an exploratory endpoint, as described above.

8. Assessment of Safety

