An additional sample size calculation was conducted for the secondary outcome of change in PCS score from baseline in the intervention group compared to the control group. Based on pooled data from the PCS development/validation studies and a French cohort of patients with RA, the population weighted mean (SD) PCS score is estimated at 20.3 (SD 12.3) (27,35,36). Thus, a clinically important difference in the PCS score, previously proposed as greater than 38% change (27,37), would correspond to a change in total PCS score of greater than 7.7/52. Aiming to exclude any (negative) effect of the intervention on change in the PCS score, we chose a non-inferiority design for this outcome. Given that the effect of the intervention on the PCS score is unknown, we chose the aforementioned minimal clinically important difference of 7.7 as the non-inferiority margin. In other words, non-inferiority will be confirmed if the upper bound of the 95% CI for the intervention's effect on PCS remains within a minimal clinically important margin(38). Following these assumptions and allowing for a 10% dropout rate, a total of 82 participants need to be included (41 in both the control and intervention groups) to demonstrate a non-inferior effect of the intervention on the PCS score with 80% power, a minimal clinically important margin and a two-sided significance level of 0.025. When 120 patients are included as per the primary outcome, and assuming a 10% drop-out rate, we should have 90.2% power to demonstrate non-inferiority for this secondary outcome.

Sample size calculations were conducted via R version 4.2.1, using the packages *pwr* and *epiR* (see Appendix B). In summary, a total of 120 patients will need to be included to assess both the primary outcome and the secondary outcome with at least 80% power, including 60 participants in both the control group and in the intervention group.

As described above, the intervention group will then again be randomized in a 1:1-ratio to assess the exploratory outcomes. The trial will thus not be powered for the exploratory analyses.

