9.2 Analysis

Analyses will be carried out according to the intention-to-treat (ITT) principle, implying that participants will be analyzed based on the group they were originally assigned to.

In this study, the ITT population will consist specifically of all patients in the intervention group who effectively downloaded and installed the Sidekick application at the baseline visit, and all patients assigned to the control group. As stated above, participants in the intervention group will be re-randomized to intervention arm A or B, constituting two additional ITT populations that will only be analyzed exploratorily.

Per protocol (PP) analyses will be carried out as sensitivity analyses, including only those patients who completed the follow-up visit.

The variables described above in sections 4-6 will be extracted from the electronic medical patient file that is employed in all participating centers (KWS). Additionally, user behavior statistics and data actively logged by the patients in the app will be collected and provided for analysis in pseudonymized form by Sidekick Health. The primary and secondary outcome data of this study will be collected via questionnaires on the MyNexuzHealth app, or if not possible in pen-and-paper format at the outpatient clinic. All study-related information will be assembled and prepared for further analysis in an electronic CRF developed in REDCap. P-values <0.05 will be considered as statistically significant for all analyses. Missing data will be handled with multiple imputation by chained equations when data can be assumed to be missing at random. Descriptive statistics for baseline participant characteristics will be provided as means (\pm SD), medians (IQR) or proportions depending on data distribution.

Primary endpoint

The difference in mean change of total ASES (Arthritis Self-Efficacy Scale) score from baseline to week 16 \pm 2w in the intervention group when compared to the control group will be evaluated with an unpaired t-test or Wilcoxon rank sum test depending on distribution of the ASES-score. As a sensitivity analysis, we will additionally assess the difference between groups in week 16 scores using ANOVA adjusted for the baseline score. Furthermore, differences in the pain and other symptoms subscales of the ASES will be presented separately.

Secondary endpoints

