- Participant engagement with the app will be analyzed descriptively as 1) the proportion of RAID questionnaires with at least one completed item in the Sidekick app, compared to the total number of RAID questionnaires prompted by the app for each participant during the study period; and 2) several user behavior statistics as described elsewhere. Additionally, participant engagement will be compared between the weekly and monthly RAID groups with unpaired t-tests or Mann-Whitney-U tests depending on data distribution.
- Candidate predictors of a favorable effect of using the Sidekick app on self-efficacy, sleep and physical activity will be studied exploratively with (multiple) linear regression.
- The evolution over time of the RAID scores at baseline, provided in the app (intervention group only) and at week 16 ± 2w, and their association with other outcomes including ASES, IPAQ-S, PSQI and DAS28-CRP/SDAI scores, will be described with linear mixed effects regression models.
- The association of data actively logged in the app (step counts, exercise activities, sleep quality, stress level, and energy level) with (changes in) the validated outcome measures RAID, IPAQ-S, PSQI, ASES, and DAS28-CRP/SDAI collected at baseline and week 16 ± 2w will be reported as Spearman or Pearson correlation coefficients depending on data distribution.

10. Quality assurance

Data collection tools and source document identification:

Source data will be collected and recorded in the study participants' files/medical records. They will be kept on a secured location at all times. The collection and processing of source data (from subjects enrolled in this study) will be limited to those data that are necessary to fulfill the objectives

of the study. These data must be collected and processed with adequate precautions to ensure confidentiality and compliance with applicable data privacy protection laws and regulations. Appropriate technical and organizational measures to protect the data against unauthorized disclosures or access, accidental or unlawful destruction, or accidental loss or alteration must be put in place. Personnel whose responsibilities require access to personal data agree to keep the data confidential.

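### App engagement, which accrues after randomisation and only in the app group, is listed as a baseline predictor of the app's effect, and no group-by-factor model is stated for the true baseline factors (minor, exploratory)

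*Combined protocol and SAP*

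**What the plan says.** **Objective.** Section 4.1 and the synopsis seek baseline predictors of the intervention's effect on four outcomes: ASES, PCS, IPAQ-S and PSQI.

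**Endpoint.** Section 4.3b and the synopsis list the candidates under the same baseline label: demographic characteristics, disease characteristics, "and measures of participant engagement (as previously defined"). The definition referred to comes just before it: the share of prompted in-app RAID questionnaires with at least one item answered over the study period, plus user-behaviour statistics such as log-ins and goals set.

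**Timing and availability.** Section 6.1, on the intervention phase, says "During this phase of the study user behavior statistics will also be collected as described above". The flowchart in section 4.6 has a row for "RAID (via Sidekick Health app, only in intervention group"). For controls the synopsis states "No access to the Sidekick Health app, and no completion of the RAID questionnaire in between study visits".

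**Analysis.** Section 9.2 says that candidate predictors of a favourable effect of app use on self-efficacy, "sleep and physical activity will be studied exploratively with (multiple) linear regression". It does not use the word baseline here, does not mention PCS, and gives no analysis population, group term or interaction.

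**Status.** Section 9.1 says "The trial will thus not be powered for the exploratory analyses". Section 9.2 also says "P-values <0.05 will be considered as statistically significant for all analyses".

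**The concern.** There are two linked problems.

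First, a variable that comes into being after randomisation, and in one group only, is listed as a baseline predictor of a randomised effect. Within the app group, patients who use the app more may also be more motivated or have a better prognosis. An association between use and improvement would then say nothing about whether use caused the improvement or whether the app works better in heavy users. The objective names baseline predictors only, so the endpoint list conflicts with it.

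Second, a predictor of the intervention's effect is a factor across which the app-versus-control difference varies. That requires controls in the model and a group-by-factor term. Section 9.2 leaves both open, so two analysts could fit different models and only one of the models would answer the objective. At stake is a statement about which patients benefit from the app that in fact describes which patients improve anyway.

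**Working it through.** **1. The plan's own figure.** No figure is stated for this analysis, so the sample size serves as the anchor. With d = 5.5/9.4 = 0.585, two-sided 0.05 and 80% power, the t-test needs 46.8 per group, or 94 in total. Then 94 × 1.10 = 103.4 (about 52 per group, as stated), and 103.4 × 1.15 = 118.9, which rounds to 119 and is taken as 120. This reproduces. Appendix B takes 108 patients after 10% dropout, so 54 per group.

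**2. Is engagement a baseline factor?** The definition (section 4.3b) runs over the study period, collection is in the intervention phase (section 6.1), and controls have no app (synopsis). Engagement has no value at randomisation and no value in controls. A group-by-engagement product term therefore cannot be estimated.

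**3. How often would a purely prognostic factor be flagged?** Suppose a baseline factor has correlation r with ASES change in both groups, and the app effect is the same for everyone. The values of r are assumptions.

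*App-group-only regression, n = 54.* Fisher's approximation gives power ≈ Φ(atanh(r) × √(n − 3) − 1.96), with √51 = 7.14:
- r = 0.2: 0.2027 × 7.14 = 1.45, about 30%
- r = 0.3: 0.3095 × 7.14 = 2.21, about 60%
- r = 0.4: 0.4236 × 7.14 = 3.03, about 86%

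Simulation of the same model gives about 31%, 61% and 85–87%.

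*Both groups, group and factor but no interaction, n = 108.* The multiplier becomes √(108 − 4) = 10.20, giving 2.07, 3.16 and 4.32, or about 54%, 88% and 99%. Adding controls without the interaction term does not help.

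*Both groups with the interaction.* The factor is flagged as an effect modifier in about 5% of simulated trials at each r, which is the nominal rate.

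**4. Engagement under the same assumptions.** Let engagement have no causal effect but correlate 0.5 with that prognostic factor. Its implied correlation with outcome is 0.5 × r, and the app-only regression flags it in about 12%, 20% and 31% of simulated trials.

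**5. Power of the model that answers the objective.** Take a 50/50 factor, so four cells of 27, and SD 9.4 (the subscale figure in section 9.1):
- interaction SE = 9.4 × √(4/27) = 3.62, against 9.4 × √(2/54) = 1.81 for the main effect
- power for a 5.5-point interaction = Φ(5.5/3.62 − 1.96) = Φ(−0.44), about 33%
- interaction detectable with 80% power = (1.96 + 0.84) × 3.62, about 10.1 points

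A 30/70 factor has 29% power and a 20/80 factor 23%. The documents give no SD for total ASES.

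**6. Side note on multiplicity.** Sections 4.3b and 4.6 name at least 6 factors (age, sex, autoantibody status, current therapy, previous therapy, disease duration). Section 6.1 lists 11 if RF and ACPA are counted separately. Section 9.2 names 3 outcomes and the objective 4. That gives 6 × 3 = 18 to 11 × 4 = 44 tests, and 0.9 to 2.2 expected chance hits at 0.05.

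**The case against.** **It is only exploratory.** The plan says so, disclaims power, and no endpoint or sample size depends on it. This stands and sets the severity. It excuses low power; it does not make engagement a baseline variable or supply the missing model.

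**Linear regression permits an interaction.** It does. A reader might infer that the plan commits to an app-users-only model. The documents do not support that: section 9.2 is silent rather than wrong. The flag rates above show what would follow from a permitted choice, not what the plan prescribes.

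**Engagement can be studied as a modifier.** A reader might infer that this is impossible. That is too strong. Complier-average or principal-stratification methods can address related questions under added assumptions. What cannot be estimated is the ordinary interaction term, and the plan names no alternative.

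**The chance-hit count is large.** It would be tempting to use it as the size of this problem. It is not: a correctly specified interaction analysis would produce the same chance hits, and section 9.2 does not commit to testing every factor against every outcome. It remains a side note.

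**Section 7 makes a causal claim.** It refers to "continued engagement with the app and its possible effects on intervention efficacy as an exploratory endpoint". The word possible already hedges it, so rewording would be editorial. Whether to exempt these tests from the general 0.05 rule is likewise a matter of preference.

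**Conclusion.** The point holds, as a minor one. The endpoint lists are wrong as written in calling engagement a baseline predictor, and section 9.2 does not state a model that would separate effect modification from prognosis.

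The size depends on how the gap is filled. An app-only model would flag a purely prognostic factor in about 31% to 87% of trials for assumed correlations of 0.2 to 0.4, against about 5% for the interaction test. These rates rest on the assumed correlations, 54 evaluable patients per group and no true effect modification; the documents supply no correlations.

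The ASES primary comparison and the PCS secondary comparison are between randomised groups and do not use these models. A reader should not infer any doubt about those conclusions from this point.

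A separate small mismatch: PCS is a target outcome of the predictor analysis in section 4.1, section 4.3b and the synopsis, but is absent from the matching sentence in section 9.2.

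**What to change.** 1. Remove engagement from the baseline-predictor lists in section 4.3b and the synopsis. Report its relation to outcome as a non-causal association within the app group, adjusted for the randomised weekly or monthly RAID arm, since arm may influence both app use and outcome. Engagement stays as its own exploratory endpoint.
2. In section 9.2, list the baseline factors and state that they are assessed in both randomised groups with a group-by-factor interaction: for example, week-16 score on baseline score, centre, group, factor and interaction. A change-score model with the same interaction would also serve. Report the interactions with 95% confidence intervals as hypothesis-generating.
3. Reconcile PCS: add it to the predictor sentence in section 9.2, or drop it from this objective and endpoint in section 4.1, section 4.3b and the synopsis.

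The cost is wording and minor programming. Section 4.4 already has the disease and demographic factors collected at baseline in all groups. The downside is low power, about 33% unadjusted for a 5.5-point subscale interaction with a 50/50 factor. Many interactions will be inconclusive, and the intervals will show that.
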